12.3 End of Treatment

The end of treatment will occur at the last day of radiation therapy and will include the weekly study assessments outlined above (see appendices).

12.4 Follow-up Period

The follow-up period will consist of a two-week period following chemoradiation treatment (or at least 30 days from the last dose of rolapitant in Sequence A) in order to identify and collect any additional toxicity during this time.

12.5 End of Study

The study will be considered complete once enrollment has been met, follow-up procedures on all subjects have been conducted, and data analysis is concluded. The study may also be terminated early for any reason by the PI-sponsor. In order to terminate the study with the Duke IRB, all data extraction and analysis must be complete. Therefore, if any articles for publication are derived from the current study, they must be submitted and accepted with no further need for additional data review prior to termination with the IRB.

Subjects that are lost to follow-up will be documented in the patient record and in the 21 CFR Part 11 compliant database (e.g. Medidata Rave). In the eCRF, the subject will be marked at "Patient Status Unknown," along with a corresponding explanation, if any. This status may also be documented on an "Off Study Form" in the eCRF.

12.6 Early Withdrawal of Subject(s)

12.6.1 Criteria for Early Withdrawal

Subjects may voluntarily withdraw from the study at any time. The PI may also withdraw a subject from the study at any time based on his/her discretion. Reasons for PI-initiated withdrawal may include, but are not limited to the following:

- Adverse events or intolerable symptoms
- Abnormal laboratory values
- Abnormal test procedure results
- Protocol deviation
- Administrative issues
- Pregnancy
- Non-compliance of the subject

12.6.2 Follow-up Requirements for Early Withdrawal

Subjects who prematurely withdraw due to toxicity will be followed for two weeks after a subject is removed from the study. End of study requirements outlined above will be conducted.

12.6.3 Replacement of Early Withdrawal(s)

Not applicable

12.7 Study Assessments

12.7.1 Medical History

Standard medical history assessments will be conducted and recorded per institutional guidelines. Past medical history will include predictors of RINV (e.g. irradiation site, planned dose, treatment field, alcohol intake, gender, age etc.). The MAT survey will capture known patient reported predictors (see appendices).

12.7.2 Physical Exam

Standard physical exam and neurological assessment will be conducted and documented per institutional and PRTBTC guidelines.

12.7.3 MASCC Antiemesis Tool (MAT)

The MAT is a validated, reliable and easy-to-use clinical tool consisting of an eight-item assessment of acute and delayed CINVCR rates.¹⁸ It was developed by the Multinational Association of Supportive Care in Cancer (MASCC) members to assist patients and oncology professionals in communicating accurately about the prevention and control of nausea and vomiting that may occur with chemotherapy. The concept of the MAT is to provide an easy-to-use and easy-to-evaluate tool to assist in providing the best individual care to patients. Additionally, the tool was designed to aid treatment centers in understanding the effectiveness of their antiemetic strategies. The internal consistency reliability of the scale was high, with Cronbach alphas of 0.77 (patient sample) and 0.82 (care-giver sample). Responses were similar between the UK and U.S. samples in terms of nausea and vomiting, and both samples found the scale easy to use. Contrasted-groups validity (using age as a grouping variable) and concurrent validity (MAT compared with Rhodes Index for nausea, vomiting and retching -INVR) suggested that the scale is sensitive to detect the different dimensions of CINV and performed well against a daily assessment of nausea/vomiting (total score correlation r=0.86, P<0.001). Recall of events was high even three weeks after chemotherapy (correlations with INVR of 0.44-0.99, all P<0.01). Factor analysis clearly identified three factors, namely vomiting, acute nausea, and delayed nausea. Proxy assessments by caregivers were congruent with the patients' responses, especially in relation to vomiting. The MAT facilitates discussion between clinicians and patients about their nausea and vomiting experience, thereby potentially aiding treatment decisions. Assessments of CINV CR rates are conducted at baseline and weekly on days 1, 2, 4 and 7, and ultimately will capture data for all days a patient is in the study (See Section 12 and appendices).

12.7.4 Treatment Satisfaction Questionnaire for Medication (TSMQ-9)

To evaluate patient preference for the combination of rolapitant plus ondansetron vs. ondansetron alone, the patients will fill out the valid TSMQ-9 questionnaire for weeks 1-3 and weeks 4-6 (see schema). Analysis of the patient satisfaction or preference endpoint can be found in Section 15.5.2.

The 14-item Treatment Satisfaction Questionnaire for Medication (TSQM) Version 1.4 is a reliable and valid instrument to assess patients' satisfaction with medication, providing scores on four scales – side effects, effectiveness, convenience and global satisfaction. In naturalistic studies, administering the TSQM with the side effects domain was thought to provoke the physician to assess the presence or absence of adverse events in a way that is clinically atypical, carrying the potential to interfere with routine medical care. As a result, an abbreviated 9-item TSQM (TSQM-9), derived from the TSQM Version 1.4 but without the five items of the side effects domain was created. In a study using an interactive voice response system (IVRS)-administered TSQM-9, it was psychometrically evaluated

among patients taking antihypertensive medication. TSQM-9 domains had high internal consistency as evident from Cronbach's alpha values of 0.84 and greater. TSQM-9 domains also demonstrated good test-retest reliability with high intraclass correlation coefficients exceeding 0.70. As expected, the TSQM-9 domains were able to differentiate between individuals who were low, medium and high compliers of medication, with moderate to high effect sizes. There was evidence of convergent validity with significant correlations with the medication adherence scale. The TSQM-9 was found to be a reliable, valid tool to assess treatment satisfaction in naturalistic study designs, in which there is potential that the administration of the side effects domain of the TSQM would interfere with routine clinical care.

13 SAFETY MONITORING AND REPORTING

The PI is responsible for the identification and documentation of adverse events and serious adverse events, as defined below. At each study visit, the PI or designee must assess, through non-suggestive inquiries of the subject or evaluation of study assessments, whether an AE or SAE has occurred.

13.1 Adverse Events

An adverse event (AE) is any untoward medical occurrence in a subject receiving study drug and which does not necessarily have a causal relationship with this treatment. For this protocol, the definition of AE also includes worsening of any pre-existing medical condition and the onset of new illness. An AE can therefore be any unfavorable and unintended or worsening sign (including an abnormal laboratory finding), symptom, or disease temporally associated with the use of rolapitant plus ondansetron vs ondansetron alone whether or not related to use of the rolapitant plus ondansetron vs ondansetron alone. But laboratory value changes that require therapy or adjustment in prior therapy are considered adverse events.

From the time the subject signs the informed consent form through the End of Study visit (as defined in Section 12.5), all AEs must be recorded in the subject medical record and adverse events case report form.

AEs will be assessed according to the CTCAE version 4. If CTCAE grading does not exist for an AE, the severity of the AE will be graded as mild (1), moderate (2), severe (3), life-threatening (4), or fatal (5).

Attribution of AEs will be indicated as follows:

- Definite: The AE is clearly related to the study drug
- Probably: The AE is likely related to the study drug
- Possible: The AE may be related to the study drug
- Unlikely: The AE is doubtfully related to the study drug
- Unrelated: The AE is clearly NOT related to the study drug

13.1.1 Reporting of AEs

Not required by sponsor

13.2 Serious Adverse Events

An AE is considered "serious" if, in the opinion of the investigator, it is one of the following outcomes*:

- Fatal
- Life-threatening
- Constitutes a congenital anomaly or birth defect
- A medically significant condition (defined as an event that compromises subject safety or may require medical or surgical intervention to prevent one of the three outcomes above).
- Requires inpatient hospitalization or prolongation of existing hospitalization
- Results in persistent or significant incapacity or substantial disruption to conduct normal life functions.

*Exception: Preplanned (at time of informed consent) hospitalization for elective procedures, for protocol compliance or social reasons, or for observation will not be considered criteria for an SAE. The reason for the planned hospitalization should be documented. Complications experienced during these hospitalizations must be reported as SAEs if hospitalization is prolonged due to AE, or if the complication meets other serious criteria.

13.2.1 Reporting of SAEs

Only adverse events that the Duke Sponsor-Investigator determines to be serious, unanticipated, and related or possibly/probably (i.e. more likely than not) related to the research must be reported to the Duke IRB. Those adverse events will be submitted in the electronic IRB system, according to the following guidelines:

- Report within 24 hours of learning about any subject's death that was unanticipated and more likely related to the research than unrelated;
- Report within 5 business days of learning about any serious, unanticipated, and related or possibly/probably related adverse event;
- Report within 10 business day of learning about any other unanticipated problem or event that was more likely related to the research than unrelated.

13.2.1.1 Reporting to TerSera

Serious adverse events that the Duke Sponsor-Investigator determines to be serious and related to rolapitant is to be shared with TerSera via MedWatch or CIOMS I form within 3 working days of Investigator awareness. If supporting documentation is included in the submission to TerSera (e.g., hospital reports, consultant reports, death certificates, autopsy reports, etc.), please redact any patient identifiers (including Medical Record number).

TerSera SAE Contact Details

Email: [contact]

• [contact]

13.2.2 Reporting Product Complaints for TerSera Products

Any written, electronic or oral communication that alleges dissatisfaction related to manufactured clinical drug product with regards to its manufacturing, testing, labeling, packaging, or shipping, must be reported by the Sponsor Institution or qualified designee to TerSera Call Center (US Call center: [contact]) within 1 working day of first becoming aware of the possible defect. This report to TerSera may also be made by telephone to the designated TerSera representative ([name]) or by fax to the Call Center ([name]). The product and packaging components in question, if available, must be stored in a secure area under specified storage conditions until it is determined whether the product is required to be returned for investigation of the defect. If the product complaint is associated with an SAE, the SAE must be reported separately in accordance with the protocol, and the SAE report should mention the product quality complaint.

13.3 Special Warnings and Precautions

Not Applicable

13.4 Safety Oversight Committee (SOC)

The Duke Cancer Institute SOC is responsible for annual data and safety monitoring of DUHS sponsor-investigator phase I and II, therapeutic interventional studies that do not have an independent Data Safety Monitoring Board (DSMB). The primary focus of the SOC is review of safety data, toxicities and new information that may affect subject safety or efficacy. Annual safety reviews include, but may not be limited

to, review of safety data, enrollment status, stopping rules if applicable, accrual, toxicities, reference literature, and interim analyses as provided by the sponsor-investigator. The SOC in concert with the DCI Monitoring Team (see Section 14.1 for Monitoring Team description) oversees the conduct of DUHS cancer-related, sponsor-investigator greater-than-minimal-risk intervention studies that do not have an external monitoring plan, ensuring subject safety and that the protocol is conducted, recorded and reported in accordance with the protocol, standing operating procedures (SOPs), Good Clinical Practice (GCP), and applicable regulatory requirements.

14 QUALITY CONTROL AND QUALITY ASSURANCE

14.1 Monitoring

The Duke Cancer Institute (DCI) Monitoring Team will conduct monitoring visits to ensure subject safety and to ensure that the protocol is conducted, recorded, and reported in accordance with the protocol, standard operating procedures, good clinical practice, and applicable regulatory requirements. As specified in the DCI Data and Safety Monitoring Plan, the DCI Monitoring Team will conduct routine monitoring after the third subject is enrolled, followed by annual monitoring of 1-3 subjects until the study is closed to enrollment and subjects are no longer receiving study interventions that are more than minimal risk.

Additional monitoring may be prompted by findings from monitoring visits, unexpected frequency of serious and/or unexpected toxicities, or other concerns and may be initiated upon request of DUHS and DCI leadership, the DCI Cancer Protocol Committee, the Safety Oversight Committee (SOC), the sponsor, the Principal Investigator, or the IRB. All study documents must be made available upon request to the DCI Monitoring Team and other authorized regulatory authorities, including but not limited to the National Institute of Health, National Cancer Institute, and the FDA. Every reasonable effort will be made to maintain confidentiality during study monitoring.

14.2 Audits

The Duke Office of Audit, Risk and Compliance (OARC) office may conduct confidential audits to evaluate compliance with the protocol and the principles of GCP. The PI agrees to allow the OARC auditor(s) direct access to all relevant documents and to allocate his/her time and the time of the study team to the OARC auditor(s) in order to discuss findings and any relevant issues.

OARC audits are designed to protect the rights and well-being of human research subjects. OARCA audits may be routine or directed (for cause). Routine audits are selected based upon risk metrics generally geared towards high subject enrollment, studies with limited oversight or monitoring, Investigator initiated Investigational Drugs or Devices, federally-funded studies, high degree of risk (based upon adverse events, type of study, or vulnerable populations), phase 1 studies, or studies that involve Medicare populations. Directed audits occur at the directive of the IRB or an authorized Institutional Official.

OARC audits examine research studies/clinical trials methodology, processes and systems to assess whether the research is conducted according to the protocol approved by the DUHS IRB. The primary purpose of the audit/review is to verify that the standards for safety of human subjects in clinical trials and the quality of data produced by the clinical trial research are met. The audit/review will serve as a quality assurance measure, internal to the institution. Additional goals of such audits are to detect both random and systemic errors occurring during the conduct of clinical research and to emphasize "best practices" in the research/clinical trials environment.

14.3 Data Management and Processing

14.3.1 Case Report Forms (CRFs)

The electronic CRF will be the primary data collection document for the study. The CRFs will be updated in a timely manner following acquisition of new source data. Only approved study staff (the PI, the research coordinators, the research nurses, the data management team, and the clinical trials manager), are permitted to make entries, changes, or corrections in the CRF.

An audit trail will be maintained automatically by the electronic CRF management system, which will be a 21 CFR Part 11 compliant database (e.g. Medidata Rave). Designated personnel will complete user training, as required or appropriate per regulations.

14.3.2 Data Management Procedures and Data Verification

Designated personnel (e.g. the data management team and the clinical trials manager) using the electronic CRF will have access based on their specific roles in the protocol.

Completeness of entered data will be checked automatically by the eCRF system, and users will be alerted to the presence of data inconsistencies. Additionally, the data management team and the statistical team will cross-reference the data to verify accuracy. Missing or implausible data will be highlighted for the PI requiring appropriate responses (i.e. confirmation of data, correction of data, completion or confirmation that data is not available, etc.).

The database will be reviewed and discussed prior to database closure, and will be closed only after resolution of all remaining queries. An audit trail will be kept of all subsequent changes to the data.

14.3.3 Study Closure

Following completion of the studies, the PI will be responsible for ensuring the following activities:

- Data clarification and/or resolution
- Accounting, reconciliation, and destruction/return of used and unused study drugs
- Review of site study records for completeness
- Shipment of all remaining laboratory samples to the designated laboratories

15 STATISTICAL METHODS AND DATA ANALYSIS

All statistical analysis will be performed under the direction of the statistician designated in key personnel. Any data analysis carried out independently by the investigator must be approved by the statistician before publication or presentation.

15.1 Analysis Sets

The analysis of the complete response endpoint will focus on all patients randomized to sequence A or B. However, the analysis of the patient preference endpoint will focus on those patients who have experienced both regimens and provided a preference assessment. Safety analyses will include all patients who receive protocol treatment.

15.2 Patient Demographics and Other Baseline Characteristics

The socio-demographic and clinical characteristics of all randomized patients will be summarized by sequence assignment using means/SD, medians, percentiles, frequencies/proportions.

15.3 Treatments

Within each sequence assignment, a frequency distribution will be generated for the number of weeks of antiemetic therapy received when ondansetron was administered alone, and when ondansetron was administered with rolapitant.

15.4 Primary Objective

The primary objective of this study is to compare the efficacy of rolapitant plus ondansetron vs. ondansetron alone in the prevention of nausea and vomiting, as measured by the overall complete response rate, among malignant glioma patients during RT and concomitant TMZ (see Section 8).

As described in Sections 15.6 and 15.7, the study was originally designed to enroll 170 glioma patients with the expectation that 160 patients would be randomized to receive one of two treatment sequences of anti-emetic therapy for the prevention of nausea and vomiting associated with RT and concomitant TMZ. A formal interim analysis was planned after 80 patients had been randomized (i.e. 40 patients to each treatment sequence). As of mid-January 2022, 53 patients had been randomized. On January 18, 2022, TerSera, the study's funding source, requested that accrual to the study be terminated in the next few months.

Given this request from TerSera, the accrual target for this study is reduced to 57 patients. The decision to terminate early has not been influenced by the data collected to date, as no interim analyses have been conducted. The analyses as described below will be conducted; however, they may no longer have the power to detect the hypothesized effect size.

15.4.1 Variable

Complete response (CR) rate associated with rolapitant plus ondansetron and that associated with ondansetron during the first two weeks of RT and concomitant TMZ is defined as the proportion of patients with no emetic episode or use of rescue medication while receiving radiation and concomitant TMZ. The CR rate will be assessed via the modified MASCC Antiemesis Tool (MAT).¹⁷

15.4.2 Statistical Hypothesis, Model, and Method of Analysis

As the primary analysis, a chi-square test will compare treatment regimens (ondansetron alone vs rolapitant + ondansetron) with respect to the proportion of patients who experience a CR during the first 2 weeks of RT and TMZ treatment. As an additional analysis, logistic regression will assess the effect of potential confounders on this relationship. Among the covariates that will be considered is the dose of decadron administered during the 2 weeks of RT and TMZ treatment.

As an exploratory analysis, a generalized linear model with a logit link that accounts for correlation between the CR status observed during the first and second treatment period within the same patient will be used to assess the impact of period, treatment, and their interaction. The purpose of this latter analysis is to assess whether the incremental effect of combination treatment relative to ondansetron alone is the same whether rolapitant is administered during the first period (i.e. first 3 weeks) or the second period (i.e. the second 3-week treatment regimen). It should be noted that this test will have low power to detect a clinically meaningful interaction effect. Within the context of the generalized linear model described above, the impact of covariates on CR rate will be explored. Included among these covariates will be the dose of decadron administer during that segment of the treatment regimen.

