9.6 Randomization

A permuted block randomization will be used to assign patients, in an unblinded fashion, to one of two treatment sequences as described in Section 9.1. A 1:1 allocation ratio will be used.

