15.7 Sample Size Calculation

15.7.1 Original Study Design

One hundred seventy (170) glioma patients will be enrolled with the expectation that 160 patients will be randomized to receive one of two treatment sequences of anti-emetic therapy for the prevention of nausea and vomiting associated with RT and concomitant TMZ. A permutated block randomization with an allocation ratio of 1:1 will be used to assign patients to sequence A or B. Sequence A involves a 3-week regimen of daily ondansetron followed by a 3-week regimen consisting of rolapitant (day 22 only) and daily ondansetron; whereas Sequence B involves a 3-week regimen of rolapitant (day 1 only) and daily ondansetron followed by a 3-week regimen of daily ondansetron. The study has one primary and one KEY secondary endpoint: CR rate and patient overall preference for ondansetron treatment with or without rolapitant. Though the primary CR rate endpoint will focus on treatment during the first 2 weeks of RT and TMZ, a crossover design is proposed so that a patient will experience both modes of treatment, and be equipped to make a comparative assessment of preference.

Power Calculations for Complete Response, Primary Endpoint: The power of the comparison of ondansetron and the combination of ondansetron and rolapitant relative to the CR rate during the initial 2 weeks of treatment with RT and TMZ will be considered here. This comparison will focus on the anti-emetic experience during the first regimen of the two treatment regimens that the patient will receive. Let

p₁ = overall complete response rate for the first 2 weeks of treatment with the combination antiemetic regimen, and

 p_0 = overall complete response rate during the first 2 weeks of treatment with ondansetron alone.

The hypothesis that will be assessed is whether the CR rate with combination treatment is greater than that with ondansetron alone. Specifically, the hypothesis that will be tested is as follows:

 H_0 : $p_1 \le p_0$ versus H1: $p_1 > p_0$

Temozolomide prescribing information reports a vomiting rate of 20% with concomitant RT + TMZ. Anti-emetic treatment failure includes the occurrence of vomiting or the use of an anti-emetic for nausea and/or vomiting. Therefore, we anticipate that approximately 25% of patients receiving ondansetron alone to either vomit or receive an anti-emetic. Equivalently, a CR rate of 75% is anticipated with ondansetron alone.

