15.7.2 Modified Study Design

As described in Section 15.4, the sample size goal for this study is reduced to 57 patients. With 57 patients, there is 80% power to detect an increase in the CR rate from 75% with ondansetron to 97% with the combination of ondansetron and rolapitant (α =0.05; one-tailed). Alternatively, there is 80% power to detect an increase in CR rate from 63% to 90%.

Relative to patient preference, with 57 patients, the study has 83% power to detect a preference rate of 69% or greater with a two-tailed test conducted at the 0.05 level of significance.

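### Section 15.4.2 applies a supportive logistic regression with an open covariate list to 57 patients, with no provision for few CR failures or an arm with none

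*Combined protocol and SAP*

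**What the plan says.** Section 15.4.2 makes a chi-square test of CR over the first two weeks the primary analysis and then adds: "As an additional analysis, logistic regression will assess the effect of potential confounders on this relationship". One covariate is named, the decadron dose given during those two weeks, and it is described only as being among those to be considered. The section does not fix the number of covariates, mention a penalised or exact form of the model, or say what is reported if one arm has no CR failures. A logit-link model for both treatment periods follows as an exploratory analysis.

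On size, section 15.7.2 says "the sample size goal for this study is reduced to 57 patients", and section 9.6 says "A 1:1 allocation ratio will be used". Section 15.4 keeps the planned analyses and warns only that they may lack power for the hypothesised effect.

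On rates, section 15.7.1 says "Equivalently, a CR rate of 75% is anticipated with ondansetron alone" and powers the original design for an increase to 90%. Section 15.7.2 then says "With 57 patients, there is 80% power to detect an increase in the CR rate from 75% with ondansetron to 97% with the combination", tested one-sided at the 5% level. It gives a second pair of rates with the same power, 63% and 90%.

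**The concern.** Logistic regression draws its information from the less frequent outcome, here CR failure. Cutting the trial from 160 to 57 leaves few failures, while the number of covariates stays open.

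A separate problem arises if no patient on the combination fails. The maximum-likelihood log odds ratio for treatment is then infinite, whatever covariates are added. Software returns a very large coefficient with a huge standard error, and the Wald test shows nothing even though the chi-square test may be clearly significant. The power caveat in section 15.4 does not cover this, because an estimate that does not exist is a different problem from an imprecise one.

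At stake is the adjusted estimate of the primary effect. If the model fails after the data are seen, the replacement method and the covariates would be chosen post hoc in an unblinded trial.

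**Working it through.** **Inputs.** N = 57 (section 15.7.2) with 1:1 allocation (section 9.6), so 28 and 29 per arm in either order. All randomized patients are in the CR analysis (section 15.1). The control CR rate is 75% (section 15.7.1). The combination rate is 90% (hypothesised, section 15.7.1) or 97% (section 15.7.2). The alternative pair is 63% vs 90% (section 15.7.2).

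**The plan's own power figure.** Pooled-variance formula, one-sided 0.05, 28.5 per arm, 75% vs 97%:

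- Null SE = √(0.86 × 0.14 × 2/28.5) = 0.0919; times 1.645 = 0.1512.
- Alternative SE = √((0.75 × 0.25 + 0.97 × 0.03)/28.5) = 0.0872.
- Power = Φ((0.22 − 0.1512)/0.0872) = Φ(0.79) = 78.5%.

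The same formula gives 78.7-78.9% for 63% vs 90%. Exact enumeration of the test gives 83.9-85.5% and 80.3-81.7%. The stated 80% is reproduced closely enough to use these scenarios.

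**Expected failures and chance of an empty arm.** Expected failures = n₀(1 − p₀) + n₁(1 − p₁). P(no combination failure) = p₁ to the power n₁. With 28 control and 29 combination patients:

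- 75/97: 28 × 0.25 + 29 × 0.03 = 7.9; 0.97^29 = 41.3%.
- 75/90: 28 × 0.25 + 29 × 0.10 = 9.9; 0.90^29 = 4.7%.
- 63/90: 28 × 0.37 + 29 × 0.10 = 13.3; 0.90^29 = 4.7%.

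**Share among significant trials.** All outcomes were enumerated with the one-sided 0.05 pooled Z test. The share is P(significant and no combination failure) divided by P(significant).

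| CR rates | Expected failures | P(no combination failure) | Share of significant trials (28/29; 29/28) |
|---|---|---|---|
| 75% vs 97% | 7.9-8.1 | 41-43% | 0.4065/0.8392 = 48%; 0.4205/0.8548 = 49% |
| 75% vs 90% | 9.9-10.1 | 4.7-5.2% | 0.0463/0.4576 = 10%; 0.0516/0.4483 = 12% |
| 63% vs 90% | 13.3-13.5 | 4.7-5.2% | 0.0471/0.8167 = 6%; 0.0523/0.8035 = 7% |

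The failure counts are expectations. With 28/29, the 10th to 90th percentiles are 5-11 (75/97), 6-14 (75/90) and 9-17 (63/90).

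**Comparison with the original design.** With 76 per arm at 75/90, expected failures were 76 × 0.25 + 76 × 0.10 = 26.6, and 0.90^76 is about 0.03%. The difficulty comes with the reduced size.

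**What an empty arm does.** Take 7 of 28 failures on control and 0 of 29 on the combination. The pooled Z is 0.25/√((50/57)(7/57)(1/28 + 1/29)) = 2.87, clearly significant. An ordinary logit fit did not converge: treatment coefficient about −25, standard error about 91,000.

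**Sensitivity.** If 95% of patients are evaluable, as in the original 152 of 160 (an assumption for the modified design), about 54 remain. At 75/97 with 27 per arm, expected failures are 27 × 0.28 = 7.6 and 0.97^27 = 43.9%.

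**The case against.** The strongest reply is that little depends on this model. The chi-square test is primary, allocation is randomized, and the test works normally when one arm has no failures. An infinite odds ratio would also be plain in the output. All of that stands, and it limits the point to an improvement of a supportive analysis.

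The text also says only that covariates will be considered, not that several enter together, and a Firth or exact fit would still count as logistic regression. That is fair. It means the text leaves the choice open, which is itself the gap to close.

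Three stronger readings are tempting and are not supported:

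- **That 97% is the trial's target, so a breakdown is close to even odds.** Section 15.7.2 gives 97% as the effect detectable with 80% power at N = 57. The hypothesised rate remains 90%, where an empty combination arm has about a 5% chance.
- **That the adjusted estimate fails in a large share of successful trials generally.** This holds at 75/97. At 75/90 and 63/90, roughly nine in ten significant trials have a failure on the combination.
- **That the cross-over model has the same failure rate.** It uses both periods, so the counts above do not apply, and the documents give no period-two CR rates from which to derive others. What can be said is structural: a model with treatment, period and their interaction has no finite maximum-likelihood interaction estimate if one treatment-by-period cell has no failures.

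**Conclusion.** The point holds as a cheap improvement to a supportive analysis. Failures are few in every scenario the plan gives, about 8 to 13 expected, against about 27 under the original design. The risk of no finite treatment odds ratio depends strongly on the true combination rate: about 5% at 90% and 41-43% at 97%. Among significant trials it ranges from 6-7% (63/90) through 10-12% (75/90) to 48-49% (75/97).

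These figures assume 28/29 allocation, all 57 patients analysed, independent outcomes and the plan's own rates. Somewhat fewer evaluable patients would make matters slightly worse. No bias in the adjusted odds ratio was calculated, so nothing is claimed about its size when it is finite. A reader might infer that the primary conclusion is at risk; it is not affected by this point.

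**What to change.** In section 15.4.2, specify Firth-penalised logistic regression with profile-likelihood intervals, or exact logistic regression, for the additional adjusted analysis. Limit it to treatment plus one or two covariates named before analysis. Corticosteroid use is one candidate, since section 12.1 already records it at screening.

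For the exploratory cross-over model, do not simply extend the Firth method, because that model must also handle within-patient correlation. State instead that it will be reported descriptively, as CR counts by treatment and period, if any treatment-by-period cell has no failures.

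The cost is a few sentences of SAP text, with no new data, visits or patients. The downside is that fewer covariates can be explored and penalised odds ratios are slightly shrunk toward the null.
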